5.1.2 Evaluable Cycle and Reference Period for Bleeding Data

Bleeding data will be analyzed by cycle and by 91-day reference period (RP). For the analysis of bleeding data by cycle, the cycle will be shifted by 3 days with the 3 days of the next cycle included in the previous cycle. For example, in the bleeding analysis Cycle 2 will be from Day 4 of Cycle 2 to Day 3 of Cycle 3 inclusive. For the 3 days after Cycle 13, the last non-missing response for bleeding in Cycle 13 will be imputed.

In determining whether a cycle is evaluable for the bleeding analysis of a specific population, the cycle based on the diary data will be used rather than the shifted cycle used to present the data.

For the ITT analysis, a cycle will be considered non-evaluable if:

• The length of the cycle is longer than 28 days.

A cycle will be considered non-evaluable in the per-protocol (PP) analysis for bleeding data if any of the following criteria are met:

- 1. A subject becomes pregnant in that cycle or prior to that cycle
- 2. The length of the cycle is shorter than 22 days or longer than 28 days
- 3. A subject did not have a hormone-free period towards the end of the cycle (i.e. there are not at least 4 days where an active tablet was not taken between the last day an active tablet was taken in this cycle and the first day an active tablet was taken in the next cycle)
- 4. The subject received unauthorized concomitant medication (see section 9.4.6.1 of the protocol) thought to have the potential to impact the bleeding analysis for at least one day during the cycle
- 5. Use of unauthorized pre-treatment and concomitant medication thought to have the potential to impact the bleeding analysis, if cycle starts within 28 days after discontinuation of unauthorized medication
- 6. The subject had a positive test for chlamydia or gonorrhea during that cycle
- 7. The subject missed 4 or more days of active pills during the cycle
- 8. The subject missed 2 or more consecutive days of active pills during the cycle
- 9. The subject had a procedure to the vagina, cervix or endometrium during the cycle

A cycle with missing diary bleeding data will still be considered evaluable if the criteria above are not met and bleeding data can be imputed for days with missing data (see Section 5.15.2 for details).

Three other analyses of bleeding data will be performed as follows:

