- 1. Using cycles in which all active pills were taken as per the instructions in the protocol. In this analysis, evaluable cycles will be defined as per the PP analysis but cycles where there was at least 1 day between Day 1 and Day 24 where an active pill was not taken will be excluded.
- 2. Using cycles in which exactly 1 active pill was missed. In this analysis, evaluable cycles will be defined as per the ITT analysis but only cycles where there was exactly 1 missed active pill between Day 1 and Day 24 are included.
- 3. Using cycles in which at least 2 active pills were missed. In this analysis, evaluable cycles will be defined as per the ITT analysis but only cycles where there were at least 2 missed active pills between Day 1 and Day 24 are included.

In addition, an analysis by RP will be performed where there are 4 91-day RPs defined as follows:

- RP1 = Day 1 to Day 91
- RP2 = Day 92 to Day 182
- RP3 = Day 183 to Day 273
- RP4 = Day 274 to Day 364

where Day 1 is the first day of Cycle 1 reported in the subject diary and then the remaining days are fixed using Day 1 as a reference. For example, Day 91 is 90 days after the date of the first day of Cycle 1.

A RP will be considered to be non-evaluable in the ITT analysis when the RP is less than 91 days in duration (i.e. where the subject withdraws from the study during the RP). If there are any gaps between cycles in

terms of date within the RP (i.e. at the end of the 4-day inactive pill period of a given cycle, the subject does not directly restart with the first active pill of the next pill pack), then the RP will be excluded from the ITT Population. For example, if Cycle 1 Day 28 is 1 February 2018 and Cycle 2 Day 1 is 3 February, then RP1 will be excluded from the ITT.

A RP with missing bleeding diary data will still be considered evaluable if the criteria above are not met and bleeding data can be imputed for days with missing data (see Section 5.15.2 for details).

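### Bleeding by missed-pill count: the zero-missed set uses per-protocol cycles and the other two sets use ITT cycles, so a reading across the three mixes pill count with unequal exclusions

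*SAP*

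**What the plan says.** SAP 5.1.2 lists three further bleeding analyses together, defined by the number of active pills missed on Days 1 to 24.

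- No pill missed: "evaluable cycles will be defined as per the PP analysis but cycles where there was at least 1 day" without an active pill are then dropped.
- Exactly one missed: "evaluable cycles will be defined as per the ITT analysis but only cycles where there was exactly 1 missed active pill" are kept.
- Two or more missed: "evaluable cycles will be defined as per the ITT analysis but only cycles where there were at least 2 missed active pills" are kept.

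The ITT evaluability rule in the same section has a single exclusion: "The length of the cycle is longer than 28 days". The PP rule has nine. They include "A subject becomes pregnant in that cycle or prior to that cycle", "The length of the cycle is shorter than 22 days or longer than 28 days" and "A subject did not have a hormone-free period towards the end of the cycle", and unauthorized medication "thought to have the potential to impact the bleeding analysis for at least one day during the cycle". The others cover unauthorized medication stopped within 28 days before the cycle starts, a positive chlamydia or gonorrhea test, two missed-pill criteria (7 and 8), and local procedures.

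SAP 9.5.3.1 repeats the same PP/ITT split for the classical cycle analysis. It also plans daily bleeding bar charts for the sets defined by active-pill count. SAP 9.0 states that no formal statistical analyses will be done.

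**The concern.** Sets labelled zero, one, and two or more missed pills form an ordered family, and readers will look across them for an effect of missed pills on bleeding. The zero-missed set differs from the other two in more than pill count, because it has also been cleaned of cycles with other reasons for altered bleeding.

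The documents themselves treat these reasons as relevant to bleeding:

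- Protocol 12.6.1 bases the PP exclusions on deviations that may affect the bleeding pattern.
- Protocol 9.6.3.6 says that chlamydia and gonorrhea can influence it.
- Protocol 9.4.6.1 says that interacting drugs may increase breakthrough bleeding.

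At stake is the interpretation of a supplementary description of cycle control. A difference from the zero-missed set could be put down to missed pills when part of it comes from the cycle-selection rules.

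**Working it through.** The plan gives no figure to reproduce, so the check is a comparison of rules followed by an illustration of scale.

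**Rules applied to each set (SAP 5.1.2)**

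| Exclusion | Zero missed | Exactly 1 | 2 or more |
|---|---|---|---|
| Cycle over 28 days (ITT rule, also in PP 2) | removed | removed | removed |
| PP 1, pregnancy | removed | kept | kept |
| PP 2, cycle under 22 days | removed | kept | kept |
| PP 3, no hormone-free interval | removed | kept | kept |
| PP 4-5, unauthorized medication | removed | kept | kept |
| PP 6, chlamydia or gonorrhea | removed | kept | kept |
| PP 7-8, missed 4 or more days, or 2 or more consecutive days | cannot occur | cannot occur | kept |
| PP 9, local procedure | removed | kept | kept |

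Apart from pill count, the zero-missed set differs from the others by criteria 1, 2 (lower limit), 3, 4, 5, 6 and 9. The one-missed and two-or-more sets share one rule. Neither SAP 5.1.2 nor 9.5.3.1 supplies a zero-missed set on the ITT rule.

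**Scale with no missed-pill effect at all**

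Let b be the rate in clean cycles, f the share of cycles that only the PP rules remove, and r the rate in those cycles. The spurious difference is f × (r − b). Neither f nor r is in the documents, so both are assumed.

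*Unscheduled bleeding.* Take b = 16.9%, the ES-C02 figure in Protocol 7.2, with f from 2% to 20% and r from 10% to 60%.

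- Lowest: 0.20 × (0.10 − 0.169) = −0.0138, about −1.4 points.
- Highest: 0.20 × (0.60 − 0.169) = +0.0862, about +8.6 points.
- An intermediate case: 0.05 × (0.25 − 0.169) = +0.0041, about +0.4 points.

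The sign depends on whether r lies above or below b.

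*Absence of scheduled bleeding.* Under SAP 5.1 the last cycle ends at the last dose, so a woman who stops mid-pack can have a short last cycle. A cycle under 22 days ends before the scheduled window opens on Day 25 (SAP 5.10.2.1). From the sample-size assumptions in Protocol 12.1:

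- Cycles per subject: 0.55 × 13 + 0.45 × 4 = 8.95.
- Last cycles of women who discontinue: 0.45 / 8.95 = 5.0% of cycles.
- Under 22 days, if stopping is uniform over the pack (assumed): 5.0% × 21/28, about 3.8%.

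Protocol 7.2 gives withdrawal bleeding of 96.5%, so absence is 3.5%. If every truncated cycle counts as absent (assumed), the rate becomes 0.962 × 3.5% + 3.8% = 7.2%. The rules alone then add 0.038 × 0.965, about 3.7 points. For f from 1% to 20% the shift runs from about 1 to 19 points. The 3.8% is a share of all cycles; the share within the one-missed or two-or-more set is unknown.

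*Pregnancy.* Criterion 1 can matter little. At the planning Pearl Index of 1.0, 12,337 at-risk cycles imply 12,337 / 1300, about 9.5 pregnancies.

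**The case against.** The strongest reply is that the SAP never sets these three analyses against each other. It states no contrast and no purpose of measuring the effect of missed pills. The zero-missed set can be seen as the strictest step in a series of ITT, PP, and PP with full intake: SAP 9.5.3.1 uses that trio for the modified cycle analysis and most subgroup summaries, without the other two sets. The one-missed and two-or-more analyses are then subsets of ITT, and SAP 12.1 records only those two as added. The outputs are named by their basis, and the listings in 9.5.3.1 give cycle inclusion, PP exclusion reasons and missed pills.

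Much of this stands. It makes the PP zero-missed analysis legitimate in its own right and keeps the point minor. It does not supply a like-for-like reference, and 5.1.2 still presents the three sets side by side.

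A second reply concerns the remedy. A reader might propose applying PP criteria 1 to 6 and 9 to all three sets, on the view that only criteria 7 and 8 conflict with missed pills. The documents do not support that view. Protocol 9.4.4.3 tells women who miss two or more consecutive active tablets on Days 18 to 24 to skip the hormone-free interval, so failing criterion 3 can be a consequence of missing tablets. For Days 1 to 17 it mentions considering emergency contraception, while 9.4.6.1 lists other contraceptive methods as unauthorized, so criteria 4 and 5 may be triggered in the same way. Excluding such cycles would remove part of what the two-or-more set should describe. This objection stands in full.

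**Conclusion.** The mismatch in evaluability rules is explicit, and it affects every comparison with the zero-missed set. It does not affect one-missed against two-or-more.

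A reader might infer that the mismatch exaggerates the benefit of full compliance. The documents do not show this. They give neither the share of cycles removed by the PP rules alone nor the bleeding rate in those cycles, and the illustrative range for unscheduled bleeding includes zero. A reader might also infer that the SAP plans a confounded formal comparison; it plans none.

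The importance is low: these are supplementary descriptive summaries of a variable classed among the other secondary ones. The percentage-point ranges show what is possible under the stated assumptions and are not estimates.

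**What to change.** Keep the PP zero-missed analysis and label it as the strict-use analysis. Add to SAP 5.1.2 and 9.5.3.1 a zero-missed analysis in cycles that meet the same ITT evaluability rule as the one-missed and two-or-more sets. State that this added set is the reference whenever results, including the daily charts, are read across missed-pill counts. Do not extend PP criteria 1 to 6 and 9 to all sets. On the existing PP zero-missed outputs, a footnote should say that the evaluability rule differs.

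The cost is a short wording change and one additional table run, using cycle flags and missed-pill counts that 9.5.3.1 already lists. With one rule throughout, the part of any difference due to unequal rules is zero by construction. Two limits remain: women who miss no pills select themselves, and SAP 5.15.1 counts a blank diary entry as no pill taken.

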5.2 Baseline and Change from Baseline

The Baseline value for each assessment is defined as the last measurement taken prior to first administration of study medication, unless otherwise stated. When the date of the assessment is on the date of first administration, it will be assumed that the assessment was performed prior to first dose. The Baseline value for the Menstrual Distress Questionnaire will be the value collected at Visit 3 because the date of completion is not collected in eCRF for this questionnaire.

For any parameter at a specific visit, change from Baseline is calculated as the value of that parameter at that visit minus the Baseline value of that parameter, as defined above.

5.3 On-Treatment Period

For contraceptive efficacy, the On-Treatment Period is defined as the period of time between the date of first dose of study medication and 7 days after the last dose of study medication (regardless of whether this is an active or inactive table), inclusive. If the subject has a pregnancy after the first dose of study medication and prior to the last dose of study medication, the On-Treatment Period is defined as the period of time between the date of first dose of study medication and the date of the estimated date of conception, inclusive. If the subject has a pregnancy when they are still on study medication but the estimated date of conception is missing because the date was not confirmed in an ultrasound, then the cycle and day of the estimated conception that is assigned from the narrative will be used to determine the end date.

For TEAEs, the On-Treatment Period is defined as on or after the date of first dose of study medication.

For medications, the On-Treatment Period is defined as the period of time between the date of first dose of study medication and the date of last dose of study medication (regardless of whether this is an active or inactive table), inclusive.

If the subject had a period of time when study medication was not being taken between the date of first dose of study medication and the last dose of study medication, this time will still be considered to be during the On-Treatment Period.

5.4 Body Mass Index

BMI in kg/m² will be calculated using the following formula:

$$BMI = \frac{weight}{height^2}$$

Weight and height collected on the CRF will not be rounded prior to deriving BMI.

5.5 Switchers, Starters and True New Users

Starters are defined as subjects who have not used hormonal contraceptives within the 3 months prior to the date of first dose of study medication.

Switchers are defined as subjects who have used hormonal contraceptives within the 3 months prior to the date of first dose of study medication.

True new users are defined as subjects who have never received a hormonal contraceptive. This group of subjects is a subset of the group of subjects classed as starters.

5.6 Prior, Post-Study Treatment and Concomitant Medication Use

Medications will be categorised as contraceptives and other medications that are not contraceptives.

For contraceptives, the medications will be classed as prior if:

- The question "Taken prior to study?" on the eCRF is answered with Y or
- The medication start date is before the date of first dose of study medication

The following contraceptive medications will be identified as concomitant contraceptives:

- Medications with a start date during the On-Treatment Period for medications (see Section 5.3 for details)
- Medications with a start date prior to the date of first dose of study medication and an end date after the date of first dose of study medication

Any contraceptives with a missing end date will be considered to be ongoing at the end of study treatment and thus would be assumed to be after the first dose of study medication and therefore assigned as a concomitant contraceptive.

Contraceptive medications can be classed as both prior and concomitant.

Contraceptives with a start date occurring after the end of the On-Treatment Period for medications will be identified as post-study treatment contraceptives. Contraceptives with a start date prior to the date of first dose of study medication and an end date on the same date as the date of first dose of study medication will be assumed to be prior only and not concomitant.

For other medications that are not contraceptives, medications with an end date occurring before the date of first dose of study medication will be identified as prior medications.

Medications with a start date occurring after the end of the On-Treatment Period for medications will be identified as post-study treatment medications.

The following medications will be identified as concomitant medications:

- Medications with a start date during the On-Treatment Period for medications (see Section 5.3 for details)
- Medications with a start date prior to the date of first dose of study medication and an end date on
 or after the date of first dose of study medication

Any medications with a missing end date will be considered to be ongoing at the end of study treatment and thus would be assumed to be after the first dose of study medication and therefore assigned as a concomitant medication.

Medications that are not contraceptives cannot be classed as both prior and concomitant.

5.7 Study Treatment Compliance

Treatment compliance for the investigational product will be assessed based on the data collected in the subject diary.

5.7.1 Compliance analysis by cycle

In the compliance analysis by cycle, a cycle will only be included if there is a reported start date for that cycle. Prior to calculating any compliance data by cycle, cycles are first determined using the start date of the cycle and the start date of the next cycle, per the rules in Section 5.1. In the compliance analysis by cycle, only days within the cycle after those rules have been applied are included in the derivation of the endpoints in this Section by cycle.

The treatment compliance will be calculated as a percentage and derived for each cycle that the subject started. For each cycle, the total number of pills (active or inactive) taken will be determined from the subject diary. If an entry of the number of active (pink) or inactive (white) pills is left blank in the diary, then it will be assumed that no pills were taken on that day.

The compliance for a given cycle will be derived as

 $100 x \frac{\text{the total number pills taken during the cycle}}{\text{the number of pills expected to be taken during the cycle}}$

The number of pills expected to be taken during the cycle is derived as the end date of the cycle – start date of the cycle + 1 where the start and end dates of the cycles are determined using the rules in Section 5.1. In the case of early termination from the study, in the last cycle for that subject, the number of pills expected to be taken during the cycle is calculated as the date of last dose of study medication – the start date of the cycle of interest + 1.

In addition, the subject diary data will be used to identify when a pill has been missed. The number of missed pills will be derived for each cycle. In this situation, a pill is assumed to be missed if there is a day in the diary without an entry for the number of tablets or with 0 active and 0 inactive pills reported as taken. Any gaps between Day 28 of a cycle and Day 1 of the next cycle will be included as missed pills. For example, if the reported start date for Cycle 1 is 1 February and the reported start date for Cycle 2 is 3 March, then the derived end date of Cycle 1 will be 2 March and 1-2 March will be included as 2 missed pills. If there are overlapping cycles in terms of dates, then the days will be included under the latest cycle and missed pills will be reported accordingly. For example, if the subject takes pills up to Day 24 in Cycle 1, then starts Cycle 2 on the same date as Day 25 of Cycle 1, so Days 25 to Day 28 of Cycle 1 will not be included in Cycle1 and these will not be counted as missed pills for Cycle 1.

5.7.2 Overall compliance

In the derivation of overall compliance, all data collected on days between the date of first dose and date of last dose will be included in the derivation. The overall compliance will be determined by summing the total number of pills (active or inactive) taken across all cycles. The overall compliance will be calculated as

$100 \ x \ \frac{the \ total \ number \ of \ pills \ taken \ across \ all \ cycles}{the \ date \ of \ last \ dose - the \ start \ date \ of \ cycle \ 1 + 1 \ in \ days}$

In the above formula, the total number of pills taken during the cycles will be the sum of pills recorded across all days between the date of first dose of study medication and the date of last dose of study medication, inclusive. For example, if there is no start date reported for Cycle 1 and there are pills reported as taken in the diary for Cycle 1, then these pills reported in Cycle 1 will not be included in the total number of pills taken as the date of first dose of study medication will be the start date reported for Cycle 2.

The total number of pills taken across all subjects will be derived by summing the number of pills taken across the study for all subjects in the Safety Population.

For drug accountability, the number of active pills dispensed will be calculated by multiplying the number of blisters dispensed by 24. The number of inactive pills dispensed will be calculated by multiplying the number of blisters dispensed by 4. The number of active and inactive pills returned will be recorded on the CRF.

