9.6.2 Efficacy Assessments

Contraceptive efficacy will be based on the Pearl Index, the method failure Pearl Index and the cumulative pregnancy rate.

On-treatment pregnancies are defined as pregnancies with an estimated date of conception within the in-treatment period (Day 1 to 7 days after the intake of investigational product, whether active or inactive tablet).

Pre-treatment pregnancies are pregnancies with an estimated date of conception before the first intake of trial medication.

Post-treatment pregnancies are pregnancies with an estimated date of conception after the intreatment period (>7 days after the intake of investigational product, whether active or inactive tablet).

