5.9.1 Pre-Treatment Pregnancies

Pre-treatment pregnancies are pregnancies with an estimated date of conception before the date of the first dose of study medication.

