5.11 Treatment-Emergent Adverse Event (TEAE)

A TEAE is defined as an AE with a start date or worsening during the On-Treatment Period for TEAEs (see Section 5.3 for definition of the On-Treatment Period).

If the start date for an AE is missing and the end date is either missing or on or after the date of first dose of study medication, then the AE will be assumed to be treatment-emergent. However, if the start date for an AE is missing and the end date is recorded and is before the first dose of study medication, then the AE will be assumed to be non-treatment emergent.

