5.15.5.2 Partial Treatment Start Dates

If the subject has a partial start date Cycle 1, and consequently a partial start date for study medication, then the partial start date will be presented in the listing. If the date of last dose cannot be derived as a result of the partial start date, then this will be blank in the listings as the end date is unknown.

In the case of an on-treatment pregnancy, the cycle of conception will be estimated from the available data. If the subject does not have an on-treatment pregnancy, then for the cumulative event rates for pregnancy, the subject will be censored in the cycle where the last pill intake was reported per the diary data. Cycle 1 will be included in the denominator for the Pearl Index following the rules in Section 5.1.1 and will be included in the bleeding analysis following the rules in Section 5.1.2.

In this case, when classifying concomitant, pre- and post medication and treatment emergent AEs and defining the Baseline assessments, the treatment start date will be assumed to be the first date in which the investigational product was dispensed. If the treatment end date cannot be determined as a result of the partial start date, then the date of last dose will be derived for the day in the diary where the last pill is reported and by assuming that the start date is the latest possible day. For example, if the partial start date is January 2017 and the last day with a pill reported is Day 4 of Cycle 1, then the assumed start date would be 31 January 2017 and therefore Day 4 of Cycle 1 would be 3 February 2017 and this would be used as the date of last dose. The diary data for pill intake will be used to derive compliance and exposure per the rules in the SAP.

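### SAP 5.7.2 dates first dose to Cycle 2 when the Cycle 1 start date is wholly missing, and 5.15.5 does not cover this case, so exposure is cut and Cycle 1 events could be classed as pre-treatment

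*SAP*

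**What the plan says.** SAP 5.7.2 defines overall compliance from the tablets recorded between first and last dose. It illustrates this with a woman for whom "if there is no start date reported for Cycle 1 and there are pills reported as taken in the diary for Cycle 1". Her Cycle 1 tablets are left out of the count because "the date of first dose of study medication will be the start date reported for Cycle 2". The denominator printed in that section runs from the start date of Cycle 1 to the last dose.

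The date of first dose is used throughout the SAP:

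- **TEAEs (5.3 and 5.11).** "For TEAEs, the On-Treatment Period is defined as on or after the date of first dose of study medication", and "A TEAE is defined as an AE with a start date or worsening during the On-Treatment Period for TEAEs".
- **Pregnancies (5.9.1).** "Pre-treatment pregnancies are pregnancies with an estimated date of conception before the date of the first dose of study medication".
- **Medications (5.6).** The split between prior and concomitant use is made at this date.
- **Exposure (5.8).** Duration is last dose date minus first dose date plus 1. The total feeds the annual TEAE rate in 9.6.1.

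SAP 5.15.1 sends missing or partial Cycle 1 start dates to 5.15.5. Sections 5.15.3 and 5.15.4 send missing study-drug dates there for classifying medications and AEs. Section 5.15.5.1 applies to women with no diary data who have an on- or post-treatment pregnancy. Section 5.15.5.2 applies to a partial Cycle 1 date. For AEs, medications and baseline, 5.15.5.2 rules that "the treatment start date will be assumed to be the first date in which the investigational product was dispensed", and 5.15.5.1 uses the same date.

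The protocol works from actual intake. In its section 9.6.2, "Pre-treatment pregnancies are pregnancies with an estimated date of conception before the first intake of trial medication". Its section 9.6.3.1 designates as TEAEs the events that occur or worsen once the product has been started.

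**The concern.** A woman with recorded Cycle 1 tablets is on treatment in that cycle. The only SAP sentence that addresses a wholly missing start date nevertheless places her first dose at Cycle 2, and nothing limits that date to the compliance calculation. The sentence gives the Cycle 2 date as the reason for omitting the tablets, so it reads as a general derivation that compliance inherits.

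The direction is also at odds with neighbouring rules. With only a month and year, 5.15.5.2 moves the start of treatment back to dispensing. With nothing at all, 5.7.2 moves it forward to Cycle 2. Elsewhere the SAP counts an AE without a start date as treatment-emergent unless it ended before first dose (5.11), and an unclear conception date as on-treatment (5.9.2). Here an event with a known date, during recorded intake, could be counted as pre-treatment. At stake are exposure totals, TEAE counts and, in principle, a pregnancy in the primary numerator.

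**Working it through.** **1. Which rule covers which case**

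| Cycle 1 situation | SAP section | Start date used to classify AEs and medications |
|---|---|---|
| No diary data, on- or post-treatment pregnancy | 5.15.5.1 | dispensing date |
| Partial start date | 5.15.5.2 | dispensing date |
| No start date, tablets recorded, Cycle 2 start reported | none in 5.15.5; only the 5.7.2 example | Cycle 2 start, read literally |

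Section 5.15.5.2 also says that Cycle 1 counts towards the Pearl Index denominator under 5.1.1. It says so only for partial dates.

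**2. Days lost.** Suppose Cycle 1 began on 1 February 2017 (not reported) and Cycle 2 began on 1 March 2017.

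- Days of recorded intake before the 5.7.2 first-dose date: 28.
- True exposure for 13 complete cycles: 13 × 28 = 364 days = 52 weeks.
- Exposure from the 5.7.2 date: 364 − 28 = 336 days = 48 weeks.

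On these figures a completer who missed no tablets would fail the 52-week exposure criterion of 5.8. An AE beginning in the 28 days precedes first dose under 5.3 and 5.11. Under the dispensing-date rule it would be treatment-emergent.

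**3. Compliance.** The 5.7.2 denominator is last dose date − Cycle 1 start date + 1. In the section's own example the Cycle 1 start date is absent, so the formula cannot be evaluated as printed.

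**4. Scale for the Pearl Index.** The plan's 12,337 at-risk cycles reproduce. With the SAP's exact Poisson limits and a true index of 1.0, the probability that the upper limit exceeds the estimate by no more than 1 is 0.940 at 12,337 cycles and 0.899 at 12,336.

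- One pregnancy changes the index by 1300 / 12,337 = 0.105.
- Ten pregnancies: 1300 × 10 / 12,337 = 1.05 (95% CI 0.51 to 1.94).
- Nine pregnancies: 1300 × 9 / 12,337 = 0.95 (0.43 to 1.80).
- With the cycles implied by the recruitment assumptions, 0.8 × (990 × 13 + 810 × 4) = 12,888, the same move is from 1.01 (upper limit 1.86) to 0.91 (upper limit 1.72).

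**5. How likely that is.** The number of affected women is not given. As an assumption, take 0.5% to 2% of 2000, which is 10 to 40 women with one first cycle each. A true index of 1.0 means 1 conception per 1300 cycles.

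- 10 / 1300 = 0.008 expected conceptions.
- 40 / 1300 = 0.03 expected conceptions.

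The change in step 4 therefore has roughly a 1% to 3% chance of arising, before any review of the pregnancy.

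**The case against.** The quoted sentence is an example inside a compliance rule. No section says that Cycle 1 events become pre-treatment. Sections 5.15.1, 5.15.3 and 5.15.4 all name 5.15.5 as the place for missing start dates, and both of its parts use the dispensing date. A programmer following that intent would keep Cycle 1 AEs treatment-emergent. This stands in part: the AE outcome is an unresolved conflict with a coverage gap. A reader might infer that the SAP has settled these events as pre-treatment; the documents do not support that.

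A reader might also infer that the primary result is at risk. There are safeguards. The investigator estimates the conception date and writes a narrative (5.9). Pre-, on- and post-treatment status is an item that may be reviewed before lock (8.3). A conception cycle confirmed in the narrative enters the denominator even if it is absent from the diary data (5.1). Silent loss of a conception is therefore unlikely. These safeguards do not change the wording of 5.9.1, and 5.15.5.2 gives no fallback start date for classifying conceptions.

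A further inference is that baseline would be taken after a full pack. This would need Visit 3 to fall exactly on Cycle 2 Day 1, within a window of Days 1 to 14. It would touch little beyond vital signs, because weight is next measured at Visit 4 and routine laboratory tests at Visit 5. It is not part of the point.

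Finally, wholly missing dates should be rare: the start date is a diary item (protocol 9.6.1), diaries are reviewed from Visit 3, and entry checks flag discrepancies (protocol 14.2). An AE that worsens after Cycle 2 starts remains a TEAE, and non-emergent AEs are still listed. All of this limits the number and visibility of cases, but does not supply the missing rule.

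**Conclusion.** The point holds as a gap and a conflict between sections. For a wholly missing Cycle 1 start date with recorded tablets, the only explicit text gives Cycle 2 as first dose, and 5.15.5 does not reach the case. Taken literally, each affected woman loses about 28 days of exposure, and her Cycle 1 adverse events, medications and conceptions could be classed as pre-treatment, against the protocol's definitions. The 5.7.2 denominator is undefined in its own example.

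The size rests on an unknown frequency. The range of 10 to 40 women is an assumption, and the 0.008 to 0.03 expected conceptions also assume a true index of 1.0 with constant risk across cycles. On those terms the primary result is unlikely to be affected. The main effect is on exposure and TEAE classification. The correction is worth making because the literal rule errs towards under-counting and costs little to repair.

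**What to change.** - **5.7.2.** Confine the Cycle 2 date to the compliance calculation, with a denominator that starts on the same date, or remove it.
- **5.15.5.2.** Extend it to a wholly missing Cycle 1 start date with recorded tablets. Use the dispensing date for AE, medication and baseline classification, as for partial dates, so that both kinds of missing date are treated alike.
- **5.9.** State that a conception during a Cycle 1 with recorded tablets is on-treatment, and that this Cycle 1 counts for the Pearl Index under 5.1.1.
- **5.8.** Derive exposure for these women from the Cycle 1 diary days, so that recorded intake is kept.

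The cost is a few SAP lines and one change to the date derivation. The downside is an imputed start date for a handful of women and possibly a few more TEAEs, because dispensing can precede the first tablet.
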